**Liver chemistry criteria for a Liver Monitoring Event and follow-up actions:**

These Increased Monitoring Criteria apply to all participants who experience a Liver Event, regardless of which treatment the participant has been randomized to.

Liver Chemistry Increased Monitoring Criteria – Liver Monitoring Event	
Criteria	Actions

ALT ≥3×ULN and <5×ULN and bilirubin <2×ULN, without symptoms believed to be related to liver injury or hypersensitivity, and who can be monitored weekly for 4 weeks.
	
 
• Notify the GSK medical monitor within 24 hours of learning of the abnormality by email or phone to discuss participant safety.
 
• Participant can continue study intervention.
 
• Participant must return weekly for repeat liver chemistries (ALT, AST, ALP, bilirubin) until they resolve, stabilise or return to within baseline.
 
• If at any time participant meets the liver chemistry stopping criteria, proceed as described above
 
• If, after 4 weeks of monitoring, ALT <3×ULN and bilirubin <2×ULN, monitor participant
 

	twice monthly until liver chemistries normalize or return to within baseline
--	--

The site will complete the liver event eCRF (Monitoring Event) in InForm and should also consider whether the AE reporting guidelines apply.

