## 2. SCHEDULE OF ACTIVITIES (SOA)

Period	Screening			Dosing						Follow-up	
Visit	1	2	3	4	5 to 10	11	12 to 16	17	18	Early Withdrawal	19
Day	(-9 to -3) A	-2 B	-1	1	2 to 7 C	8	9 to 13 C	14	15		28 (± 7)
Documentation of Positive GeneXpert and/or TB smear (TB clinic/site of initial diagnosis)	X										
Written Informed Consent	X										
Demography (including smoking history)	X										
Medical & Treatment History	X										
Inclusion/Exclusion/Eligibility Assessment	X										
Chest X-ray	X										
Physical Examination D	X			X	X	X	X	X	X	X	X
Vital Signs E	X	X	X	X	X	X	X	X	X	X	X
12-Lead ECG	X								X	X	X
Randomisation M		X									
Echocardiogram (may be conducted at any of the screening visits)	X									X S	X S
Blood PK F							X F	X	X	X	
Spot Sputum (confirm TB & adequate bacterial load) G	X										
Rifampicin Resistance Test (rapid) G (microscopy and GeneXpert tests may be repeated on an overnight sputum sample if needed)	X										
Haematology, Clinical Chemistry, Urinalysis H	X			X	X	X		X		X	X
Cardiac safety biomarkers T	X			X	X			X			
Urine Drug Screen I	X	X I									

Period	Screening			Dosing						Follow-up	
	1	2	3	4	5 to 10	11	12 to 16	17	18	Early Withdrawal	19
Visit											
Day	(-9 to -3) A	-2 B	-1	1	2 to 7 C	8	9 to 13 C	14	15		28 (± 7)
HIV Test (and CD4 Count if HIV confirmed)	X										
CCI				X	X			X		X	
				X	X			X		X	
			X					X			
Hospital Admission	X B	X B									
Overnight Sputum L	X	X	X	X	X	X	X	X			
IP Administration and Compliance Check N				X	X	X	X	X			
Mycobacteriology Assessments O		X	X					X			
Hospital Discharge									X	X	
Concomitant Medication		X	X	X	X	X	X	X	X	X	X
Adverse Events P				X	X	X	X	X	X	X	X
Point of Care Blood Glucose or HbA1c Q			X					X			

- A. The Visit 1 (day -9 to -3) time period will be up to a maximum of 7 days but will be kept as short as possible.

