- B. Participants can proceed with the Visit 2 (day -2) assessments as soon as their Visit 1 (day -9 to -3) assessments have been completed i.e. Visits 1 and 2 may occur on the same day as long as the screening results are available in time for randomisation. Participants may be hospitalised during the entire pre-treatment period if the Investigator considers it advisable for reasons of safety or compliance.
- C. All events listed as occurring on Visit 5 (day 2) to Visit 10 (day 7) and Visit 12 (day 9) to Visit 16 (day 13) will be conducted each day during these visits.
- D. Height (m) will only be collected once at Visit 1 (day -9 to -3). A full physical examination will be performed at Visit 1 (day -9 to -3), with symptom-directed physical examinations at Visit 17 (day 14), Visit 19 (day 28) and Early Withdrawal Visit (EWV). Symptom directed physical examinations may be conducted as required during the study (visits 4 to 16). Requirements for the physical examination are specified in the SRM.
- E. Systolic blood pressure (SBP) and diastolic blood pressure (DBP) (mmHg), heart rate (beats per minute [bpm]), body temperature (°C), respiratory rate (breathes per minute) and weight (kg). To be performed within 4 hours prior to the first daily dosing on Visit 4 (day 1) through to Visit 17 (day 14) and within 4 hours before the time dosing would have occurred on Visit 18 (day 15). On days where the following assessments are done the order should be: vital signs before blood draws for PK or safety assessments.
- F. PKs will be performed as noted in the PK table. A single pre-dose PK sample will be collected on each of Days 12 & 13, and serial PK blood sampling will occur on Day 14 (see PK table below). At EWV a PK sample will be taken before the time of the planned daily dosing. If this is not possible, a spontaneous PK sample will be taken.

- G. Sputum smear microscopy and molecular rapid test for confirmation of Mycobacterium tuberculosis and rifampicin susceptibility (GeneXpert). If the first spot sputum or overnight sputum sample shows an unfavourable result, the tests may be repeated on a freshly collected spot sputum or overnight sputum sample and that result used instead.
- H. ). Refer to [Appendix 3](#) for details.
- I. Urine drug screen: cocaine, amphetamines and opiates. Urine drug screen can be repeated at Visit 2 (day -2) for participants who were not hospitalized at Visit 1 (day -9 to -3).
- J. CCI
- K. [REDACTED]

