### 3.3.2. Benefit Assessment

Mouse models predict efficacy at human equivalent exposures consistent with the upper doses being tested. Nevertheless, efficacy of GSK3036656 has not been demonstrated in humans and no benefit can be expected from receiving the compound over the 2-week course of the study, and as monotherapy. A significant proportion of people with TB fail treatment (~15% with drug-sensitive up to ~80% with XDR). New effective compounds with novel mechanisms of action are urgently needed for TB, and it is recognised as a priority area by the WHO. The results of this study will establish whether GSK3036656 has activity, tolerability and safety adequate to take into subsequent studies of longer duration with the intention of developing a medicine for TB with a novel mechanism of action that could form part of a new combination treatment regimen for TB.

A delay of treatment with the full standard regimen of 14 days is not expected to have an adverse impact on the ultimate cure of TB in these participants, and this approach has been used as part of recent successful TB drug development programs ([Diacon, 2011b](#), [Diacon, 2013](#)). Participants in this study will have their TB infection carefully characterized and drug sensitivity profiles established.

Participants will remain under constant medical attention and will be housed and monitored in hospital from admission through the duration of the treatment period; this will allow the continuous monitoring of the health conditions of each participant, any of whom can be withdrawn at any stage of the trial and removed from study treatment should his/her condition suggest to the Investigator that this would be in his/her best interest. Multiple blood samples will be taken for safety laboratory studies. Upon discharge, the participants will be given the initial doses of standard TB treatment and immediately referred to the national TB treatment program local TB clinic where they will receive a full course of standard treatment. At the follow-up visit it will be confirmed that this treatment has been initiated and is being continued. The Investigators' primary responsibility is to ensure participant safety.

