#### **9.4.5. Clinical Safety Laboratory Assessments**

- Refer to [Appendix 3](#) for the list of clinical laboratory tests to be performed and to the SoA for the timing and frequency.
- The Investigator must review the laboratory report, document this review, and record any clinically significant changes occurring during the study in the AE section of the CRF. The laboratory reports must be filed with the source documents. Clinically significant abnormal laboratory findings are those which are not associated with the underlying disease, unless judged by the Investigator to be more severe than expected for the participant's condition.
- All laboratory tests with values considered clinically significantly abnormal during participation in the study or within 24 hours after the last dose of study treatment should be repeated until the values return to normal or baseline or are no longer considered significantly abnormal by the Investigator or medical monitor.
- If such values do not return to normal/baseline within a period of time judged reasonable by the Investigator, the aetiology should be identified and the Sponsor notified.
- All protocol-required laboratory assessments, as defined in [Appendix 3](#), must be conducted in accordance with the SRM and the SoA.

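### For ALT of 3 to under 5 times ULN, Appendix 7 allows dosing to continue with weekly repeats; after a qualifying Day 8 value the next dated ALT is the routine Day 14 sample.

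*Protocol*

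**What the plan says.** Protocol Appendix 7 (Section 13.7) defines a liver monitoring event as ALT at least 3 but under 5 times ULN, with bilirubin under 2 times ULN, no liver-type or hypersensitivity symptoms, and weekly follow-up feasible for four weeks. It applies to both arms. The medical monitor must be told within 24 hours. On dosing, the text is permissive: "Participant can continue study intervention". On repeat testing: "Participant must return weekly for repeat liver chemistries (ALT, AST, ALP, bilirubin) until they resolve, stabilise or return to within baseline". The stopping rules stay in force: "If at any time participant meets the liver chemistry stopping criteria, proceed as described above".

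In the Schedule of Activities (Protocol Section 2), the row "Haematology, Clinical Chemistry, Urinalysis" is marked on Day 1, Days 2 to 7, Day 8 and Day 14 of the dosing period. It is blank for Days 9 to 13, and the copy in SAP Section 12.2.1 shows the same blank. Footnote C makes a mark in the Days 2 to 7 column a daily assessment. ALT belongs to this panel (Appendix 3, Table 2).

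Section 9.4.5 adds a general rule that clinically significant abnormal values "should be repeated until the values return to normal or baseline or are no longer considered significantly abnormal by the Investigator or medical monitor". It gives no interval.

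**The concern.** Weekly repeats suit outpatients on a long course. Here the course is 14 days and participants are "housed and monitored in hospital from admission through the duration of the treatment period". A seven-day interval is half the treatment period, and the routine chemistry schedule thins out at the point where a late signal would need following. A participant with a known ALT rise on Day 8 then has the same dated samples as one whose ALT is normal.

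The stop at ALT of 5 times ULN needs a laboratory result to act on. The issue matters on both arms: Appendix 7 itself names raised liver enzymes and hepatitis as listed side effects of the standard-of-care tablets. What is at stake is individual safety during a few days of dosing, not the efficacy analysis.

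**Working it through.** The plan states no figure to reproduce; the check is a count of days.

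**Inputs**
- Routine on-treatment chemistry: Day 1, Days 2 to 7 daily, Day 8, Day 14 (Protocol Section 2, footnote C).
- Monitoring-event repeat: every 7 days (Appendix 7).
- Dosing: once daily, Days 1 to 14.
- Assumption: the weekly clock starts at the first qualifying value. Appendix 7 does not say.

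**Rule.** For onset on day d, the dated checks are the routine days after d plus d + 7, up to Day 14.

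| Onset d | d + 7 | Dated checks after d | Longest gap (days) |
|---|---|---|---|
| 1 | 8 | 2–8, 14 | 6 |
| 2 | 9 | 3–9, 14 | 5 |
| 3 | 10 | 4–8, 10, 14 | 4 |
| 4 | 11 | 5–8, 11, 14 | 3 |
| 5 | 12 | 6–8, 12, 14 | 4 |
| 6 | 13 | 7, 8, 13, 14 | 5 |
| 7 | 14 | 8, 14 | 6 |
| 8 | 15 | 14 | 6 |

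For onset on Day 1, 7 or 8 the weekly repeat lands on a day that already has routine chemistry, or after the last dose. It adds nothing on treatment, and the interval from Day 8 to Day 14 is 14 − 8 = 6 days. If the clock instead restarted at a persisting Day 8 value, every onset day would show this 6-day gap.

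**Doses in the gap.** Days 9 to 13 are 5 doses; 5/14 = 35.7% of the course. The Day 8 dose is a sixth if the Day 8 sample is taken before it.

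**Sensitivity.** If the Days 2 to 7 column meant a single draw on Day 3 or 4, a Day 8 value would still have only Day 14 after it, so the gap stays at 6 days.

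**With a shorter repeat, for a value persisting from Day 8**

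| Spacing | Extra samples | Longest gap (days) |
|---|---|---|
| 72 h | 1 (Day 11) | 3 |
| 48 h | 2 (Days 10, 12) | 2 |
| 24 h | 5 (Days 9–13) | 1 |

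At 72-hour spacing, two doses fall on the days between consecutive checks.

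**The case against.** A reader might infer that the protocol keeps a participant with a liver signal on drug for six days with no check required. The documents do not support that.

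- Continuation is allowed, not directed, and the medical monitor is contacted within 24 hours to discuss safety. Section 8.1.1 also requires discontinuation below the thresholds if the investigator judges it best for the participant.
- Section 9.4.5 already asks for a repeat of clinically significant values. Whether a given ALT qualifies is the investigator's judgement, but 3 times ULN is both the screening exclusion limit (Section 6.2) and the SAP's clinical-concern threshold (Section 12.8.1). A repeat is probably called for; only its date is open.
- The limit of 5 times ULN is not the only stop. ALT of at least 3 times ULN with new or worsening liver or hypersensitivity symptoms also stops drug. A participant in this band already meets the ALT half, so a symptom report can trigger the stop without a new sample. Adverse events and vital signs are recorded daily on Days 9 to 13.
- Appendix 3 allows extra tests at any time.

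These points lower the risk substantially. What remains is that none of them dates an ALT before Day 14, and an asymptomatic rise is visible only on a sample.

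Two further objections have force. Section 8.1.1 refers to an algorithm covering increased monitoring, and that figure is absent from the text supplied; the Study Reference Manual is also unavailable. Either could hold a shorter interval. And the 72-hour limit is borrowed from the stopping-event part of Appendix 7, where events outside the bilirubin and INR criteria get one repeat within 24 to 72 hours and then weekly follow-up. Repeating it here samples a milder event more often. The reason is that drug is still being given, but that is a judgement.

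**Conclusion.** The point stands as a cheap, minor improvement to participant safety. On the readable text, a qualifying ALT on Day 8, whether new or persisting from onset on Day 1 or Day 7, has no dated follow-up until Day 14: 6 days and 5 doses. For onset on Days 2 to 6 the longest gap is 3 to 5 days if the weekly clock runs from onset.

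The conclusion assumes that neither the unseen Section 8.1.1 figure nor the Study Reference Manual sets a shorter interval. It does not extend to a claim that hepatotoxicity would be missed. The documents give no ALT kinetics, so the chance of crossing 5 times ULN within the gap cannot be estimated. Entry excludes ALT of 3 times ULN or more, and the readable risk rows in Section 3.3.1 name no hepatic risk for GSK3036656 (part of that table is redacted). The event should be rare, and in-patient care makes an earlier repeat likely. The primary endpoint and the sample size are unaffected.

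**What to change.** Add one sentence to the Liver Monitoring Event actions in Appendix 7:

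*While dosing continues, repeat ALT, AST, ALP and bilirubin within 72 hours of each on-treatment ALT of at least 3 times ULN and apply the stopping criteria to each result; after the last dose, repeat weekly.*

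If the Section 8.1.1 figure already gives a shorter interval, copy that into Appendix 7 instead, so that the two agree.

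For a persisting Day 8 value the cost is one extra blood draw at about Day 11, or two at 48-hour spacing. Participants are already in hospital, so no visits or participants are added. Sharing a needle-stick is possible only on the GSK3036656 arm on Days 12 and 13, where "A single pre-dose PK sample will be collected on each of Days 12 & 13"; it does not help on Day 11 or on the standard-of-care arm, which has no PK sampling. Section 9 also lets time points for planned safety assessments be added with documented approval and without a protocol amendment, should the sponsor prefer that route.

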## 13.9. Appendix 9: Protocol Amendment History

The Protocol Amendment Summary of Changes Table for the current amendment is located directly before the Table of Contents (TOC).

### Amendment 4 (17-FEB-2021)

#### Overall Rationale for the Amendment:

- To allow for Standard of Care medication administered in the study to be either Rifafour e-275 or an equivalent generic alternative.
- Addition of 'e-275' to all references to Rifafour, for consistency.
- To allow for analysis of the primary endpoint data to be performed on additional cohorts.

#### CHANGES

#### Synopsis / Overall Design:

A single-centre, open-labelled, clinical trial in up to five sequential cohorts of participants with rifampicin-susceptible tuberculosis (DS-TB). Each cohort will involve participants being randomised to one of two possible treatments: either GSK3036656 or Standard-of-care (SoC) regimen for DS-TB (**i.e. Rifafour e-275 or equivalent generic alternative**). The ratio of participants assigned to GSK3036656 vs Rifafour **e-275 (or equivalent generic alternative)** will be 3:1.

#### Schedule of Activities / PK sampling time and events table:

[figure not shown]
- C. PK sampling is only to be performed on participants receiving GSK3036656. PK samples will not be taken from participants receiving Rifafour **e-275 (or equivalent generic alternative)**.

## 5. Study Design / Overall Design

The study will comprise up to 5 cohorts of participants. It is intended that 15 participants in each cohort will receive GSK3036656 and 5 will receive standard-of-care regimen for DS-TB (**i.e. Rifafour e-275 or equivalent generic alternative**). There will be no placebo in this study. The study will be randomized, but not blinded (i.e., it will be 'open-label') with neither participant nor Investigator blinded to treatment. Study participants will revert to the standard treatment for TB (**i.e. Rifafour e-275 or equivalent generic alternative**) once the study treatment (Day 1 to Day 14) has been completed. All laboratory staff involved in analysing and reporting the primary and secondary change in log10CFU counts and TTP endpoints results will be blinded to treatment allocation. Cohorts will proceed sequentially starting A through D, with preliminary safety, tolerability and pharmacokinetic data from the previous cohort reviewed prior to selecting the dose for the next cohort

## 5.2 Study Schematic

\*This is not part of the study but is the post-study definitive treatment of TB.

Rifafour e-275 or equivalent generic alternative.

## 5.4 Participant and Study Completion

Following completion of the study treatment phase and after discharge from hospital the participants will be provided with their first dose/s of standard TB therapy (**i.e. Rifafour e-275 or equivalent generic alternative**) with appropriate counselling. All participants will be referred to the local community TB clinics to receive the remainder of a full course of standard antituberculosis chemotherapy according to national guidelines. The participants will be provided with a referral letter to take with them to the TB clinic. Within a week of the participant's discharge from the study clinic, a follow-up call will be made by the study site staff to the TB clinic to determine if the participant attended the clinic.

## 5.5 Scientific Rationale for Study Design

The Rifafour **e-275 (or equivalent generic alternative)** treatment group is included as a benchmark for the EBA quantitative mycobacteriology and to evaluate whether HRZE in this population gives similar EBA results to that demonstrated in prior studies with this combination. A negative control arm, where subjects are left untreated, would be unethical due to the availability of effective treatment and the consequences of not treating TB.

## 7.1 Treatments Administered

Study Treatment Name:	GSK3036656	Rifafour e-275 (or equivalent generic equivalent)
Dosage formulation:	Capsule	Tablet
Unit dose strength(s)/Dosage level(s):	1 mg or 5 mg or 25 mg GSK3036656 capsules (as free base equivalent)	Standard dose: 150/75/400/275 mg of Rifampicin, Isoniazid, Pyrazinamide and Ethambutol respectively per tablet
Route of Administration	Oral	Oral
Dosing instructions:	Refer to study reference manual	Refer to South African National TB Treatment Guidelines (including pyridoxine as required)
Packaging and Labelling	Study Treatment will be provided in HDPE bottles. Each HDPE bottle will be labelled as required per country requirement.	Will be provided by the manufacturer.
Manufacturer	WuXi AppTec (1 and 5 mg capsules) Aptuit (25 mg capsule)	Rifafour e-275: Sanofi-Aventis or appropriate alternative Equivalent Generic alternative to Rifafour e-275: Appropriate suppliers

**Rifafour e-275 (or equivalent generic alternative).**

Some participants will be treated with standard, intensive phase pulmonary TB treatment as recommended in the SA National TB Treatment Guidelines to verify that the laboratory assays used measure the expected magnitude of activity. This is HRZE (Rifafour e-275 or **equivalent generic alternative**) (HRZE: H=isoniazid: R=rifampicin: Z=pyrazinamide: E=ethambutol). The Rifafour **e-275 (or equivalent generic alternative)** treatment group is included as a benchmark for the EBA quantitative mycobacteriology and to evaluate whether HRZE in this population gives similar EBA results to that demonstrated in prior studies using this combination.

Rifafour e-275 (**or equivalent generic alternative**) Package Insert contains its known and potential risks and benefits.

## 8. Discontinuation Criteria

If this results in the patient being placed on standard of care (**i.e. Rifafour e-275 or equivalent generic alternative**), then all assessments relevant to Rifafour **e-275 (or equivalent generic alternative)** will be performed as directed by the protocol (for example, GSK3036656 pharmacokinetic assessments are not required, since the participant is not being dosed with GSK3036656).

## 11. Dose Escalation

The primary endpoint may be analysed for all available cohorts after the final visit of the last subject on the second consecutive cohort that reaches or exceeds the target PK plasma exposure for efficacy (based on the murine infection model), **and subsequent cohorts**. The purpose of this efficacy analysis is to optimise dosing for subsequent cohorts (e.g. to help estimate the dose response curve) as well as to aid internal decision making.

### 13.7 Appendix 7: Liver Safety: Required Actions and Follow-up Assessments

Elevated liver enzymes, transient liver dysfunction, hepatotoxicity and hepatitis are listed as side-effects in the package inserts for Rifafour e-275 (see References) **or equivalent generic alternative**, associated with multiple drug components. Therefore, participants allocated to Rifafour e-275 (**or equivalent generic alternative**) treatment who experience Liver Chemistry Stopping criteria are not mandated in the first instance to undergo those follow-up assessments (which are intended to investigate aetiology). The investigations may still be performed, if required in the judgement of the investigator.

